5.9. Statistical analysis plan

The statistical analysis will be divided into two parts, one descriptive and one analytical. The descriptive part will consist of showing counts and fractions of categorical variables and central tendencies (mean + standard deviation or median + interquartile range) of continuous variables recorded at the beginning of the follow-up by the groups of major interest. The groups of major interest are formed by the indication of implantation and the type of implant (primary augmentation
Silimed Indústria de Implantes Ltda

[name]

[contact] **[contact]

www.silimed.com.br • [contact] • facebook: silimed international/brasil

with textured surface implant, primary augmentation with polyurethane foam-coated surface implant). In addition, for the purpose of exploring heterogeneity this approach will also be done by participant center.

The initial statistical analysis for the analytical part is to estimate the risks (cumulative probabilities up to a follow-up time) and their respective confidence intervals of unwanted (expected and not expected) events in general and interest-specific ones (e.g. capsular contracture in the textured implants group, in the polyurethane implants group, mild events, serious events, events with probable causality, etc.), as well as events of different intensities (mild, moderate, severe, etc.). The accumulated risks up to the first events in the period of interest will be estimated through the Kaplan-Meier estimator. This analysis should consider the patient as an observation unit, and then the same approach will consider the breast as an observation unit.

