5.10. Minimum sample size

The minimum sample size was estimated considering the variations of safety outcomes considered clinically relevant in the primary breast augmentation groups in different studies with a 3-year follow-up. It would be interesting to consider event risk estimates over 10 years because of the study follow-up plan. However, the risks available in the literature are rarely reported in 10 years or it is not possible to be sure that all volunteers have been followed for 10 years or more. It was possible to find only one study with a 9-year accumulated risk assessment with Silimed® products [36], which indicates that the risks of implant rupture are 4.3% and 1.2%, that the capsular contracture risks are 12.0% and 14.4%, that the risks of removal of the implant were 13.9% and 36.4%, and that the risks of any reoperation were 22.2% and 47.9%, always in the primary augmentation and primary reconstruction groups respectively. In this way, we also considered the risk accumulated in 3 years of previous studies that were used to register similar products and that the risks between the implant types are equivalent.

The events considered relevant were: need for reoperation for any reason, removal of the implant without replacement, removal of the implant with replacement, capsular contraction grade III or IV and implant rupture initially having a study of 3 years of follow-up and as a measure of interest to be estimated at a given time event, in the example of 3 years of follow-up. We used the epiDisplay package of R-project software that has a function with a formula that indicates the probability of the event of interest in the population and the formula returns the minimum sample size (N). [37] In addition, we determined the additional arguments of the formula, which are the population size for which the results would be inferred as infinity, the significance as 5%, and the difference between the estimated probability and one of the limits of the confidence interval (accuracy) as follows: if the probability to be estimated between 0.30 and 0.70, the desired accuracy = 0.1; If the probability is between 0.10 and 0.30, or between 0.70 and 0.90, the desired accuracy would be = 0.05; If the probability to be estimated is less than 0.10 or greater than 0.90, the desired accuracy would be half the probability or half of the probability respectively.

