With the reoperation as a result, it was decided that the probability to be estimated could vary between 10% and 18%, which would lead to a minimum sample N of 138 to 227 volunteers. Still in the **Silimed Indústria de Implantes Ltda**

[name]

[contact] [contact]

www.silimed.com.br • [contact] • facebook: silimed international/brasil

same group having as an outcome the removal of the implant without replacement, it was decided that the probability to be estimated could vary between 0.5% and 3% which would take the minimum sample N between 3099 and 558. For the implant removal outcome with replacement, it was judged that the probability to be estimated could range from 5% to 25% by making the minimum sample N vary between 81 and 753 still in the primary augmentation group. As for the capsular contracture outcome, it was estimated that the probability to be estimated could vary between 2% and 10%, making the minimum sample N vary between 138 and 753.

Considering that the study will follow a larger follow-up than the example above, and that the risk of these events will accumulate, and that the highest and lowest risk of events observed in 9 years were respectively 1.2% and 47.9 % [36], the minimum sizes for desired accuracy in the primary augmentation groups would be 246 volunteers, that is, 246 volunteers in the textured implant group and other 246 in the polyurethane implant group. Finally, if we consider a loss of follow-up of 40% over 10 years, the total sample size should be increased from 492 to 700 (proportionally distributed between the 2 groups). In conclusion, a sample of 350 volunteers in the textured implant group and another 350 in the polyurethane implant group.

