In the event of loss of follow-up greater than planned, there will be no replacement, i.e. there will be no further inclusions or substitutions throughout the study, nor interruption of the study. In this case, it must be considered if the loss of follow-up is differential, which may lead to errors in the final estimates of greater interest, or non-differential, and may only lead to loss of precision in the estimates. In the first case, since the outcome in the observed period will be unknown, it would be reasonable to explore the possibilities of uninterrupted participants presenting and not presenting the outcomes of interest, and in these two scenarios to see if there are relevant differences that modify the interpretation. In the second case, what should occur is the loss of accuracy of the estimates beyond that expected in the period after the loss of follow-up is greater than expected. Vagueness may disrupt the interpretation of results in the final periods of observation but will not invalidate interpretation in previous periods.

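### A check for outcome-related loss to follow-up is specified only if loss exceeds the planned 40%, an allowance set for precision and not for bias

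*Combined protocol and SAP*

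**What the plan says.** Section 5.9 makes the primary estimator explicit: "The accumulated risks up to the first events in the period of interest will be estimated through the Kaplan-Meier estimator". It states no assumption about censoring and names no sensitivity analysis for women whose outcome is unknown.

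Section 5.10 sizes the study with a loss allowance: "if we consider a loss of follow-up of 40% over 10 years, the total sample size should be increased from 492 to 700". The next paragraph opens with a condition: "In the event of loss of follow-up greater than planned, there will be no replacement". The question about bias follows from that condition: "In this case, it must be considered if the loss of follow-up is differential, which may lead to errors in the final estimates of greater" (in part). If the loss is judged differential, the section suggests two scenarios, one in which the lost women have the outcome and one in which they do not. It words this as a sensible thing to do, not as a requirement. If the loss is judged non-differential, only precision is said to suffer.

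Elsewhere, section 8.3 undertakes that lost data will be accounted for and analysed when noticed, without naming a method. The quality indicators in section 5.12 count visits made within their windows but do not list loss by implant group.

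**The concern.** Section 5.10 itself separates loss that produces error from loss that costs only precision. It then uses a precision quantity, the sample-size allowance, to decide when to ask about error. The two are not linked. Loss of 20% can bias a Kaplan-Meier risk if the women who leave are those with problems, and loss of 50% can leave it unbiased if leaving is unrelated to outcome.

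If the study runs to plan, up to 40% of women may be lost with no specified look at whether that loss is related to events. Some link is plausible. Section 6.5.1 lists implant removal or replacement, and other aesthetic breast interventions, among the reasons for withdrawal. Section 5.5.2 foresees women taking an event to another professional. The annual safety alarms in section 5.11 use the same Kaplan-Meier risks, so an understated risk would also make an alarm less likely.

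**Working it through.** **The plan's own figures.** The precision formula n = 1.96² p(1−p)/d² with p = 0.20 and d = 0.05 gives 245.9, which matches "246 volunteers in the textured implant group and other 246 in the polyurethane implant group". The value p = 0.20 is inferred; the document does not state it. The step from 492 to 700 is close to 492 × 1.4 = 689, whereas 492/(1 − 0.40) = 820. So the 40% enters only as an inflation of a precision-based sample size. (Separately, 1 − 492/700 = 29.7%, so 700 keeps 492 women only up to about 30% loss.)

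**Reading the condition.** The only planned loss figure is the 40% over 10 years. The opening condition of the paragraph and the back-reference in the bias question together mean that the question is asked above 40% and not otherwise. Sections 5.9, 5.11, 5.12, 6.5.1, 7 and 8.3 supply no loss analysis at or below that level.

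**Illustration of size.** The documents give only the 9-year augmentation risks (section 5.10: contracture 12.0%, removal 13.9%, reoperation 22.2%) and the 40%. The rest is assumed: constant hazards, a loss hazard that would reach 40% at 10 years if no event intervened, and a hazard after loss equal to r times that of followed women.

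For removal:
- Event hazard h = −ln(1 − 0.139)/9 = 0.01663 per year.
- Loss hazard l = −ln(1 − 0.40)/10 = 0.05108 per year.
- Kaplan-Meier limit = 1 − exp(−10h) = 15.3%.
- True risk = 1 − exp(−10(h+l)) − I, where exp(−10(h+l)) = 0.50808, I = l·exp(−10rh)·[1 − exp(−10a)]/a and a = h + l − rh.
- I = 0.35445, 0.33872, 0.32388, 0.30986 and 0.28411 for r = 0.5, 1, 1.5, 2 and 3.

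| 10-year risk | Reported | r = 0.5 | r = 1 | r = 1.5 | r = 2 | r = 3 |
|---|---|---|---|---|---|---|
| Removal | 15.3% | 13.7% | 15.3% | 16.8% | 18.2% | 20.8% |
| Reoperation | 24.3% | 21.9% | 24.3% | 26.5% | 28.5% | 32.0% |
| Contracture | 13.2% | 11.9% | 13.2% | 14.5% | 15.8% | 18.1% |

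At r = 2 the gap for removal is 18.2 − 15.3 = 2.9 points. The simulated standard error with 350 women is about 2.2 points, and the design's target half-width for risks of 10% to 30% is 5 points.

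**A second model.** Let the lost women carry k times the hazard throughout, with loss times uniform over 10 years, 40% lost, and a 10-year removal risk of 13.9% in retained women. Kaplan-Meier then gives 16.7% against a true 18.7% (k = 2), 19.3% against 22.8% (k = 3), and 12.3% against 11.2% (k = 0.5). The gaps are somewhat smaller or larger but follow the same pattern.

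**The plan's two scenarios.** Under the first model at 40% loss, no removals after loss gives h/(h+l) × (1 − 0.50808) = 0.2456 × 0.4919 = 12.1%. A removal in every lost woman gives 1 − 0.50808 = 49.2%.

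**The case against.** The strongest reply is that the paragraph sits in the sample-size section and says what follows when the allowance fails; it does not forbid looking at loss below 40%. That is right. A reader might infer that the risks will be reported as unbiased, or that loss will never be examined. The documents say neither. What stands is that no loss analysis is pre-specified at or below the plan.

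The protocol also has real safeguards: diaries that capture care elsewhere (5.5.2), half-yearly telephone contacts (6.4.2), outcome data still to be collected after discontinuation (6.5.1), and active search with home visits (7). These may well reduce outcome-related loss. They do not show what the remaining loss does to the estimates.

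Further inferences go beyond the text:
- **Unequal loss escapes the trigger.** Loss of 25% in one implant group and 55% in the other averages (0.25 × 350 + 0.55 × 350)/700 = 40%. It goes unchecked only if the 40% means total loss. Section 5.10 applies it to the total but also sizes each group, and read per group, 55% would trigger the check.
- **Unequal loss creates a false difference between implants.** The illustration does not show this. With that split and r = 2, both groups report 15.3%, while the modelled true removal risks are 17.1% and 19.5%. That contrast arises because the model raises a woman's hazard once she is lost.
- **Loss of about 14% by year 3 is the planned pace.** It is 1 − exp(−3l) under constant loss. The documents give no pace, so the fair point is that nothing says how to judge loss against the plan at an annual analysis.
- **The bias favours the product.** Its direction depends on r, for which the documents give no value.

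**Conclusion.** The point holds as a trigger set on the wrong quantity. Section 5.10 recognises outcome-related loss as a source of error but provides for examining it only above 40%, a figure chosen for precision. At or below 40% no check is specified for the primary Kaplan-Meier risks. If the 40% is total loss, imbalance between implant groups could also go unchecked.

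The size is conditional. With 40% loss and lost women at 1.5 to 3 times the hazard, the removal risk is understated by 1.5 to 5.5 points (15.3% against 16.8% to 20.8%). It is unbiased at a ratio of 1 and overstated by 1.6 points at 0.5. At a ratio of 2 the gap exceeds one standard error but lies inside the 5-point target half-width. Because neither sign nor size can be known in advance, the check should not depend on the amount of loss. This should be changed, but it does not invalidate the design.

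**What to change.** In section 5.10, remove the condition that loss must exceed the plan. At each yearly report and at the final analysis, whatever the amount of loss and separately for each implant group:

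1. Report the amount of loss.
2. Compare lost with retained women on data already collected: baseline characteristics, last satisfaction and BEQ scores, and prior adverse events.
3. Run the section's existing event-present and event-absent scenarios for lost women beside the Kaplan-Meier risk, preferably with intermediate excess-hazard values between the extremes, and state whether the interpretation changes.

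Keep 40% as a precision benchmark only. A censoring-weighted Kaplan-Meier estimate may be added as an option. It corrects only for loss explained by measured variables and would leave the unexplained excess hazard modelled above, so it does not replace the scenarios.

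The cost is a change of wording and some extra programming for each report; no new data, visits or participants are needed. The downside is wide ranges at the two extremes (12.1% to 49.2% for removal in the illustration), which is why intermediate values help.

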5.11. Intermediate analysis

Intermediate analyzes with generation of progress reports should always occur once a year, throughout the duration of the study, in the month following the first recruitment. Interim reviews shall consist of the same analyzes provided for in the analysis plan for the final report unless the

Silimed Indústria de Implantes Ltda

[name]

[contact] **[contact]

www.silimed.com.br • [contact] • facebook: silimed international/brasil

number of participants included up to the time specified in the report does not allow this. At first, as the study is not randomized and interventions are already recorded for routine clinical use, as well as there is a greater interest in long-term safety-related events, there is no intention of early interruption of the study as a whole for safety reasons or benefit evident between the different implants to be studied. However, there is a need to indicate in the interim reports whether or not there are differences in the rates of safety-related events between participating centers that merit greater attention from the sponsor and possible need for corrective measures.

The table below contains the limit reference values for the comparison of cumulative risks to be estimated by the Kaplan-Meier method. Risks will be compared as proportions and the alarm will be given if there is a significance difference at 1%. The reference limits were refereed considering data from the literature with implants of the brand SILIMED and reports of registration of similar products. In the literature, the risk of capsular contracture with SILIMED implants varies in the different studies, but is usually low (1% in 10 years [39], 0.40% in 15 years [40], 8.8% in 5 years [41], 11.2% at 8 years [42], 12% at 9 years [38]). The risk of surgery for implant removal is also low (1.2% for 15 years [40], 16% for 5 years [41], 12% for 8 years [42], 13.9% for 9 years [38]). With these values, an initial core trend value was estimated, i.e. from the first year, a risk of 5% was added. For the following years, i.e. from the second to the tenth year of follow-up, a threshold value was added which indicates the cumulative increase in risk for each event. The initial limits of comparison considered were 6.30%, 6.85% and 5.65% for capsular contracture, removal with replacement and removal without replacement, respectively. The progressive increase for each of these three events are: 1.00%, 1.25% and 0.175% per year.

Table - Reference limits of the risk of event to alarm in the intermediate evaluations.

Year	Capsular contracture	Removal with replacement	Removal without replacement
1	6,30%	6,85%	5,65%
2	7,30%	8,10%	5,83%
3	8,30%	9,35%	6,00%
4	9,30%	10,60%	6,18%
5	10,30%	11,85%	6,35%
6	11,30%	13,10%	6,53%
7	12,30%	14,35%	6,71%

Silimed Indústria de Implantes Ltda

[name]

[contact] [contact]

www.silimed.com.br • [contact] • facebook: silimed international/brasil

8	13,30%	15,60%	6,89%
9	14,30%	16,85%	7,07%
10	15,30%	18,10%	7,25%

5.12. Quality criteria for data management and periodic reports.

Data quality should be verified in a stratified form, and the following indicators are considered as minimum elements, including quality indicators.

1. Total number of participants since the beginning of the recruitment, and number of participants in the previous 30 days.
2. Number (fractions) of visits made within the windows provided from the beginning and in the last 30 days.
3. Number (fractions) of fields with missing or inconsistent data.
4. Number (fraction) of CRFs finalized up to 3 business days after the end of the visit window from the beginning of the study and in the last 30 days.
5. Number (fractions) of adverse events not closed up to 6 months after initial event record.
6. Number (fraction) of adverse events, serious adverse events and grade 3, grade 4 or unclassifiable from the start of the study and the last 3 days.

6. Procedures of the study

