- Inflammation or irritation: response of the body to an external infection or aggression, which is characterized by redness, edema, heat or pain. Detected through inspection and physical examination.
- Lymphedema or lymphadenopathy: enlargement and engorgement of the lymph node (s), usually leading to edema resulting from lymph stasis. It can be identified on physical examination, especially if compared to a contralateral structure.
- Implant malposition: occurs when the implant is poorly positioned in the initial surgery. If implantation was considered adequate first and there was displacement, the event should be recorded as displacement (see above).

Silimed Indústria de Implantes Ltda

[name]

[contact] [contact]

www.silimed.com.br • [contact] • facebook: silimed international/brasil

- Need for surgical removal of a capsule or scar (unacceptable scarring): The location of the incision or envelope may progress to an aesthetic result that does not look like healthy or expected skin.
- Need to remove the implant: removal of the implant will be considered a consequence, i.e. an additional therapy of a previous adverse event. It will not be considered an adverse event if it is performed only and exclusively at the request of the patient.
- Necrosis: cell death of tissues. Necrosis has several classifications according to the pathogenesis. It can usually be clinically identified by inspection because of the typical appearance or odor, or additional vascular findings.
- Ripple: The surface of the breast presents with ripples. It can be identified by physical examination.
- Palpability or visibility of the implant: the implant becomes visible or perceptible to the touch.
- Paresthesia or hyperesthesia of the breast or nipples: abnormal sensation (e.g. numbness or itching) or acute sensations with no apparent cause such as pain, heat, cold or touch. Usually identified when informed by the patient during physical examination.
- Ptosis: Flaccidity and sagging of the breast, usually identifiable by inspection.
- Rash: a rash or efflorescence on the skin.
- Implant rupture: a hole or tear in the implant housing that allows the implant filling material, its contents, to escape from the housing. The ruptures may be intracapsular (within the capsule of the scar tissue surrounding the implant) or extracapsular (outside the scar tissue around the implant).

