- Seroma: Similar to a hematoma, it occurs when the aqueous portion of blood is collected around a surgical incision or around a breast implant. Depending on its size and extent it may be identified on the physical examination, and additionally on the image (e.g. tomography, MR or US).

In case of reoperation, the frequencies of the reasons that led to reoperation within each initial indication will be studied, mainly if the reoperation was motivated by cosmetic / cosmetic reasons or not. In case of explantation, the following aspects will be investigated: (1) indication for explantation, (2) which adverse events were involved that culminated in the indication of explantation, (3) clinically relevant observations at the time of explantation (e.g. appearance of the capsule, gross defects, general conditions of the implants, etc), (4) if capsulectomy was performed, (5) discoloration and

Silimed Indústria de Implantes Ltda

[name]

[contact] [contact]

www.silimed.com.br • [contact] • facebook: silimed international/brasil

amount of extrusion content, (6) presence and extent of rupture, seroma, hematoma, inflammation or ALCL, (7) condition and appearance of the capsule. Silimed® will gather the information available from each explanation and will perform the procedures of analysis of removed implants.

For some selected adverse events (most frequent), the risk of recurrence of the same adjusted / stratified events by the type of treatment of the first event will be estimated. The most frequent events that need treatment are expected to be capsular contracture. The capsular contractures will be classified according to Baker's classification that considers whether the implant was for primary augmentation or for reconstruction. [31,32]

Table. Baker's classification for capsular contracture after breast augmentation surgery.

Class 1	Absolutely natural breasts. No one notices that there was an increase of the breasts.
Class 2	Minimal contraction. It is possible to note that surgery was performed, but patient does not present complaints.
Class 3	Moderate contracture: Patient notices hardening.
Class 4	Evident contracture. Apparent only by observation.

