Visit 2: The following procedures will be performed – 60 days after implantation (window of + or - 30 days)

- Return of adverse event diary and evaluation of completion.
- Complete physical examination by the physician.
- Assessment and guidance on possible adverse events and conduct.
- Application of patient's and evaluator's quality of life and satisfaction questionnaires.
- Delivery of the adverse event diary and guidance on its use and completion.
- Scheduling the return to the research center, 180 days after implantation.

Visit 3: The following procedures will be performed – 180 days after implantation (window of + or - 30 days)

- Return of adverse event diary and evaluation of completion.
- Complete physical examination by the physician.
- Evaluation and guidance on possible adverse events and conduct.
- Application of patient's and evaluator's quality of life and satisfaction questionnaires.

Silimed Indústria de Implantes Ltda

[name]

[contact] [contact]

www.silimed.com.br • [contact] • facebook: silimed international/brasil

- Delivery of the adverse event diary and guidance on its use and completion.
- Scheduling the return to the research center, 365 days after deployment.

Visit 4: The following procedures will be performed – 365 days after implantation (window of + or - 30 days)

- Return of adverse event diary and evaluation of completion.
- Complete physical examination by the physician.
- Application of patient's and evaluator's quality of life and satisfaction questionnaires.
- Evaluation and guidance on possible adverse events and conduct.
- Delivery of the adverse event diary and guidance on its use and completion.
- Scheduling the return to the research center, 365 days after deployment.

Visit 5, 6, 7, 8, 9, 10, 11, and 12: The following procedures will be performed – 2, 3, 4, 5, 6, 7, 8, 9 years after implantation (window of + or - 60 days)

- Return of adverse event diary and evaluation of completion.
- Complete physical examination by the physician.
- Application of patient's and evaluator's quality of life and satisfaction questionnaires.
- Evaluation and guidance on possible adverse events and conduct.
- Delivery of the adverse event diary and guidance on its use and completion.
- Scheduling the return to the research center, 360 days after deployment.

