The names and identities of the participants will be kept confidential by the Principal Investigator and his/her team and by the research monitor. No information will be provided outside the research center without the participant's permission. The data entry system has a series of controls and rules that prevent incoming out-of-format data, inconsistent data, and blank field submission. As well as a monitoring and calling tool for checking extreme, unusual or unverified data. Even so, professionals must be able to properly fill out data collection forms, since data entry essentially minimizes typing errors and not fill-in errors.

13. Expected outcomes

It is expected from this investigation that Silimed® products are of similar safety or safer than literature data indicate, when compared to the results of the Silimed® products themselves prior to commercialization, or when compared to results of similar products from competing manufacturers. That could elucidate which groups of patients could be at greater risk of adverse events or that allow to discuss in what moments/conditions there could be additional interventions to reduce the known events. In addition, the beneficial effect of the implants is expected to be equivalent to or above a desired measure.

Silimed Indústria de Implantes Ltda

[name]

[contact] **[contact]

www.silimed.com.br • [contact] • facebook: silimed international/brasil

14. Execution Schedule:

Activities and indicators of progress	Time				
	2017	2018	2019	2020 to 2028	2029
- Submission of the project to the IRB	X	X			
- Inclusion of patients after approval of the research project by the Research Ethics Committee and notification to ANVISA		X	X*		
- Presentation of the partial analysis of the data collected			X	X	
- Presentation of the final analysis of the data collected					X

* If the total number of participants is not reached in the year 2018, the recruitment may be extended until 2019. After the "N" of the study (700 participants in total) is reached, the inclusion will be interrupted, not being possible to include any volunteer, not even in case of loss of follow-up throughout the study.

Silimed Indústria de Implantes Ltda

[name]

[contact] [contact]

www.silimed.com.br • [contact] • facebook: silimed international/brasil

15. Bibliography

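### With no imaging scheduled, the planned implant rupture estimate is a lower bound, and a value below the literature figures may reflect missed ruptures

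*Combined protocol and SAP*

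**What the plan says.** Section 5.10 closes its list of relevant events with "capsular contraction grade III or IV and implant rupture initially having a study of 3 years of follow-up". The other events are reoperation and removal with and without replacement. It then cites a nine-year report on the sponsor's products, "which indicates that the risks of implant rupture are 4.3% and 1.2" (per cent, for primary augmentation and reconstruction in that order). The table in Section 2.3 gives 6.9% at 7 years for a textured comparator in augmentation, and 0.0% to 3.0% at 3 years across three comparators.

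Section 5.5 defines the event anatomically: "Implant rupture: a hole or tear in the implant housing that allows the implant filling material, its contents, to escape from the housing". It separates intracapsular from extracapsular rupture but does not say how either is found. The entry for seroma, by contrast, reads "Depending on its size and extent it may be identified on the physical examination, and additionally on the image (e.g. tomography, MR or US". Calcification, cyst and hematoma also mention imaging.

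The visit procedures in Section 6.4 list "Complete physical examination by the physician", adverse-event evaluation and return of the diary. They schedule no imaging, and the instruments in Section 6.1 include no imaging form.

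Several other routes to detection are stated:
- active enquiry at each assessment, stressed for expected events, with an abnormal complementary test counting as an adverse event (5.5.1);
- diary entries checked against medical records (5.5.2);
- presence and extent of rupture noted at explantation, and analysis of removed implants by the sponsor (5.5);
- further exams at the physician's discretion (6.3);
- participants asked to report care received elsewhere (Section 7).

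The yearly reports repeat the final analyses (5.11), so a rupture estimate with its interval is implied, although Section 5.9 does not name rupture. The alarm limits are: "The initial limits of comparison considered were 6.30%, 6.85% and 5.65% for capsular contracture, removal with replacement and removal without replacement, respectively". Section 13 expects that the sponsor's "products are of similar safety or safer than literature data indicate".

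**The concern.** The listed routes reach ruptures that cause symptoms, change the examination, happen to be imaged, or are seen when the implant comes out. The plan does not claim that questioning or examination can reveal a tear contained within the scar capsule. If recorded ruptures are genuine, the expected estimate cannot exceed the true risk, and it falls short by whatever share is missed.

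That matters because of the comparison in Section 13. For rupture, under-detection pushes the result towards similar or safer. Nothing in the plan records how many women were in a position to have a rupture found, so a low figure cannot be separated into low risk and low detection. Imaging history not asked about at the time may be hard to recover at year 10.

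**Working it through.** **Inputs.** 350 women per group, 246 before allowance for loss, and 40% loss over 10 years (5.10), so 350 × 0.6 = 210 remain. Reference risks are 4.3% at 9 years (5.10) and 6.9% at 7 years (2.3). The documents give no detection share. I assume 50%, 70% and 100% in this study and, at first, 100% behind the cited figures.

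**The plan's precision rule.** n = 1.96² p(1−p)/d². For p = 10%, d = 5 points: 3.8416 × 0.09/0.0025 = 138, as stated. For p = 2%, d = 1 point: 753, as stated. No size is given for rupture. Under the same rule, p = 4.3% and d = 2.15 points give 3.8416 × 0.04115/0.000462 = 342. With 350 women the half-width is 2.1 points, and with 210 it is 2.7. Random error is thus near what the plan accepts elsewhere. Detection is the open issue.

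**Reported risk.** Reported risk = true risk × share found. A true 4.3% is reported as 4.3 × 0.7 = 3.0% or 4.3 × 0.5 = 2.15%. A true 8.6% at 50% detection is reported as 4.3%.

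**Chance that the 95% interval lies wholly below 4.3% when the true risk is 4.3%.** I use exact (Clopper-Pearson) intervals and treat the 9-year risk as a simple proportion. The second column is the largest count whose upper limit is under 4.3%. The remaining columns are the binomial probability of that count or fewer.

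| Women per group | Ruptures found, at most | All found | 70% found | 50% found |
|---|---|---|---|---|
| 210 | 3 | 1.9% | 12.1% | 33.7% |
| 246 | 4 | 1.8% | 13.5% | 38.9% |
| 350 | 7 | 1.6% | 17.2% | 52.0% |

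**Against 6.9% at 7 years, true risk 6.9%.** The cut-offs are 7, 9 and 14 ruptures. The chances are about 2% with all found, 20–28% at 70% and 56–77% at 50%.

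**True risk doubled to 8.6%.** The interval lies above 4.3% from 16, 18 and 24 ruptures. This happens in 73–90% of cases with all found, 20–28% at 70% and about 2% at 50%.

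**If the cited study also missed ruptures.** Suppose it found 80% and this study finds 70%. The true risk matching a cited 4.3% is 4.3/0.8 = 5.4%, reported here as 5.375 × 0.7 = 3.8%. The interval then lies below 4.3% in 4–5% of cases. With equal shares the bias cancels and the chance returns to under 2%.

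**Would an alarm row help?** An exact one-sided 1% test against 4.3% needs 25 ruptures in 350 women or 17 in 210. Its power for a true 8.6% is 86% and 64% with full detection, but 1% in both at 50% detection. Raised by 5 points, as Section 5.11 does for other events, the limit would be 9.3%, and it would fire for that doubling about 0.2% of the time at year 9.

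**The case against.** A reader might infer that rupture has no reference figure and no route to detection. The documents do not support either reading. Sections 2.3 and 5.10 give rupture risks, and the 1.2% named as a bound in the final sizing is itself the rupture risk in reconstruction. Active enquiry, diary, explantation findings, discretionary exams and reports of outside care are all stated, so a rupture seen on outside imaging can already be recorded. These routes are partial, because none reaches a silent rupture that nobody has imaged.

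The contrast among definitions should not be pressed. Several others, such as extrusion and rash, also name no method. FORM 11 is completed at on-site visits, but its content is not described, so it may already ask about imaging.

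The strongest objection is that the magnitude rests on assumed shares and on sources not available here. That stands. The figures show sensitivity to detection, not an estimated bias. Section 13 also states an expectation and defines no test, so reading an interval wholly below the reference as safer is my device.

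Finally, an estimate restricted to imaged or explanted women cannot correct the low figure, since they are selected partly on suspicion of rupture. That also stands, and it limits the fix.

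**Conclusion.** The concern holds in a limited form. Rupture is a named relevant event that will be estimated from enquiry, examination, chance or discretionary imaging, and explantation. The estimate is a lower bound, and a value below 4.3% at 9 years or 6.9% at 7 years does not by itself show lower risk. The size is unknown. With 50–70% found here and all found in the cited study, a device at exactly 4.3% would look safer in about 12–52% of cases. With equal detection the figure is under 2%.

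One might also infer that the missing alarm row is the defect. It is not: any reoperation has no row either, the table is a chosen subset, and a rupture row would do little if half the ruptures go unseen. Nor do the documents show that ruptures will in fact be missed at any particular rate. This is an inexpensive improvement worth considering, not a flaw that invalidates the analysis.

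**What to change.** 1. At each on-site visit, record whether the breasts have been imaged since the last visit and whether rupture was seen, unless FORM 11 already does so.
2. In each yearly and final report, give the number of women imaged or explanted in each group beside the rupture estimate.
3. Label the estimate 'detected rupture (no scheduled imaging)', and state that a value below the literature figures is not read as lower risk unless detection was comparable.

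Any estimate restricted to imaged or explanted women should be descriptive only. No scheduled imaging and no alarm limit are asked for.

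The cost is one added case-report item at visits already planned, one count per group in the reports and a sentence of text. Imaging history would be partly self-reported, and rupture risk could be claimed only as a lower bound.
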